1 GLOSSARY OF ABBREVIATIONS

Abbreviation	Description
ADaM	Analysis Data Model
AE	Adverse Event
ALP	Alkaline Phosphatase
ALT (SGOT)	Alanine Aminotransferase
ANC	Absolute Neutrophil Count
ANCOVA	Analysis of Covariance
AST (SGPT)	Aspartate Aminotransferase
AUC	Area Under the Curve
AUC _{0-t}	Area Under the Plasma-Concentration Time Curve from Zero Up to the Last Measurable time point
AUC _{0-inf}	Area Under the Curve from Zero extrapolated to infinite time
BUN	Blood Urea Nitrogen
bpm	Beats per minute
CFB	Change from Baseline
CK	Creatinine kinase
CM	Concomitant Medication
C _{av}	Average concentration during the dosing interval
C _{max}	Peak Drug Concentration
C _{min}	Lowest observed plasma concentration in the dosing interval
C _{trough}	Plasma concentration at the end of the dosing interval
CRAC	Calcium Release Activated Calcium Channel
CRF	Case Report Form
CSR	Clinical Study Report
CTCAE	Common Terminology Criteria for Adverse Events
ECG	Electrocardiogram
eCRF	Electronic Case Report Form
FSH	Follicular Stimulating Hormone
GGT	Gamma Glutamyl Transpeptidase
HCV	Hepatitis C Virus
HIV	Human Immune Deficiency Virus
Hr	Hour
HV	Healthy Volunteers

Abbreviation	Description
ICH	International Conference on Harmonization
IMP	Investigational Medicinal Product
LAR	Late Phase Asthmatic Response
LPS	Lipopolysaccharide
K_{el}	Apparent terminal elimination rate constant
MAD	Multiple ascending dose
MCH	Mean Corpuscular Hemoglobin
MCHC	Mean Corpuscular Hemoglobin Concentration
MCV	Mean Corpuscular Volume
MedDRA	Medical Dictionary for Regulatory Activities
mmHg	Millimeters of mercury
MMSE	Mini Mental State Examination
MTD	Maximum Tolerated Dose
PCP	Phencyclidine
PFT	Pulmonary Function Test
PI	Principal Investigator
PK	Pharmacokinetic
PR	P wave, R wave interval
PT	Preferred Term
QRS	Q wave, R wave, and S wave complex
QTcB	QT wave complex corrected for heart rate using Bazette's formula
SAD	Single ascending dose
SAE	Serious adverse event
SAP	Statistical Analysis Plan
SAS	Statistical Analysis System
SDTM	Study Data Tabulations Model
SOC	System Organ Class
SOP	Standard Operating Procedure
SRC	Safety Review Committee
$t_{1/2}$	Half life
TEAE	Treatment Emergent AE
T_{max}	Time of C_{max}
K_{el}	Terminal Rate Constant

2 INTRODUCTION

The purpose of this statistical analysis plan (SAP) is to provide a thorough description of statistical methods and presentation of the study data to be used for the analysis of data generated from the Single Ascending Dose (SAD) part and the Multiple Ascending Dose (MAD) part of the clinical trial described in protocol: “An integrated Phase I/IIa, randomized, double-blind, placebo controlled study to evaluate the safety, tolerability and pharmacokinetics of single and multiple ascending dose(s) of oral RP3128 (CRAC channel modulators) in healthy volunteers and to evaluate the effect on Late Phase Asthmatic Response(LAR) to allergen challenge in patients with mild asthma.”

This SAP is based on protocol RP3128-1601 Final Version 2 dated 22March2017. This document provides the detail statistical analysis plan for the SAD part and the MAD part of the protocol.

The SAP includes details of data handling procedures and statistical methodology. The SAP also provides the shells for the Tables, Listings, and Graphs (TLGs) to be delivered to Rhizen Pharmaceuticals SA, Inc.

The final statistical analysis will proceed in accordance with this SAP as approved by both Rhizen Pharmaceuticals SA and Inflamax Research Limited. Any deviation from this SAP will be documented in the final Clinical Study Report (CSR).

For this study, the Study Data Tabulation Model (SDTM) as well as the Analysis Data Model (ADaM) specifications will be prepared by Inflamax Research and provided to the Sponsor. SDTM Model 1.4 and SDTM Implementation Guide (SDTM IG) version 3.2 will be used. ADaM Model 2.1 and ADaM Implementation Guide (ADaM IG) version 1.0 will be used. SDTM/ADaM datasets will be provided separately for SAD and MAD parts.

The following documents were also reviewed in preparation of this SAP:

- Electronic Case Report Form (eCRF) SAD Final Version 1.0 dated 31OCT2016
- Electronic Case Report Form (eCRF) MAD Final Version 1.0 dated 31OCT2016
- eCRF Completion Guidelines SAD&MAD Final v1.0 dated 31OCT2016
- Data Management Plan Final v1.0 dated
- Codelist Details dated 28OCT2016
- Safety Monitoring Committee charter, version 2.0, dated 21DEC2016

3 TUDY OBJECTIVES

The study objectives related to the SAD and MAD portion of the trial are described below.

3.1 PRIMARY OBJECTIVE

- Part 1 (SAD) - to investigate the safety and tolerability of single ascending oral doses of RP3128 in Healthy Volunteers (HV).
- Part 2 (MAD) - to investigate the safety and tolerability of once a day multiple ascending oral doses of RP3128 at three dose levels (highest safe doses identified in SAD) in HV.

3.2 SECONDARY OBJECTIVE

- Part 1 (SAD) - To characterize the pharmacokinetic (PK) profile of single ascending oral doses of RP3128 in HV.
- Part 2 (MAD) - To characterize the multiple dose PK profile of oral RP3128 at steady state when administered once day, at three dose levels in HV.
- Part 2 (MAD) - To evaluate ex-vivo effect of RP3128 on various biomarkers (Th1, Th2 and Th17 cytokines) following Lipopolysaccharide (LPS) or CD3/CD28 stimulation.

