3.3 BRIEF DESCRIPTION

This is a phase I, single-center, double-blind, randomized, placebo-controlled study to evaluate the safety, tolerability, and PK of single or multiple ascending dose (SAD or MAD) of RP3128 in healthy volunteers.

There were 5 cohorts in SAD and 3 cohorts in MAD. In the first part of the study (Part 1, SAD), single dose of RP3128/placebo was administered on Day 1. In the second part (Part 2, MAD), multiple doses of RP3128/placebo were administered once a day from Day 1 to Day 7. In both SAD and MAD, the cohorts were dosed sequentially so that a minimum of 8 days was allowed between dose of previous cohort and the initiation of next cohort. Progression to the next higher dose occurred only after confirming safety, tolerability and PK of existing dose. In case of safety concern, additional subjects may be added to cohort for safety assessment as per the decision of Safety Review Committee (SRC).

In addition, sentinel design was applied. Within each cohort, 2 sentinel subjects was dosed first for safety assessment. Safety and tolerability data up to 24 hours was reviewed along with any observation up to 36 hours by the investigator prior to dosing the remaining subjects at that dose level. The remainder of the cohort was dosed sequentially at least 48 hours after confirming safety and tolerability of sentinel cohort.

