4.2 SECONDARY ENDPOINTS

The secondary endpoints include PK parameters and biomarker assessments

SAD-PK Endpoints:

- Maximum observed plasma concentration (C_{\max})
- Time to maximum observed plasma concentration (T_{\max})
- Area under the plasma concentration-time curve from time zero until the last time point with measurable concentration (AUC_{0-t})
- Area under the plasma concentration-time curve from time zero to infinity (AUC_{0-inf})
- Apparent termination elimination rate constant (K_{el})
- Apparent terminal elimination half-life ($t_{1/2}$)

MAD-PK Endpoints:

- Maximum observed plasma concentration in the dosing interval (C_{\max}) (Day 1, Day 7)
- Lowest observed plasma concentration in the dosing interval (C_{\min}) (Day 7)
- Plasma concentration at the end of the dosing interval (C_{trough}) (Day 3, Day 5, Day 7)
- Average concentration during the dosing interval (C_{av}) (Day 7)
- Time to maximum plasma concentration (T_{\max}) (Day 1, Day 7)
- Area under the plasma concentration-time curve from time zero until the last time point with measurable concentration (AUC_{0-24}) (Day 1, Day 7)
- Degree of fluctuation [$(C_{\max}-C_{\min})/C_{av}$] (Day 7)
- Swing [$(C_{\max}-C_{\min})/C_{\min}$] (Day 7)
- Terminal half-life ($t_{1/2}$) (Day 1, 7)

MAD-Biomarker Endpoints:

- Levels of various biomarkers (Th1, Th2 and Th17 cytokines) following LPS or CD3/CD28 stimulation

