8.3 DERIVED DATA AND HANDLING OF MISSING OR BELOW LLOQ DATA

8.3.1 Derivation of PK Parameters

PK parameters for RP3128 will be derived with validated SAS programs for all RP3128 dose levels by non-compartmental analysis of the plasma concentration data using actual sampling times.

The following pharmacokinetic variables will be derived:

SAD:

- Maximum observed plasma concentration (C_{max})
- Time to maximum plasma concentration (T_{max})
- Terminal half-life ($t_{1/2}$)
- Area under the plasma concentration-time curve from time zero until the last measurable time point (AUC_{0-t})
- Area under the plasma concentration-time curve from time zero to infinity time (AUC_{0-inf})
- Elimination rate constant (K_{el})

MAD:

- Maximum observed plasma concentration in the dosing interval (C_{max}) (Day 1, Day 7)

- Lowest observed plasma concentration in the dosing interval (C_{\min}) (Day 7)
- Plasma concentration at the end of the dosing interval (C_{trough}) (Day 3, Day 5, Day 7)
- Average concentration during the dosing interval (C_{av}) (Day 7)
- Time to maximum plasma concentration (T_{max}) (Day 1, Day 7)
- Area under the plasma concentration-time curve from time zero until the last time point with measurable concentration (AUC_{0-24}) (Day 1, Day 7)
- Degree of fluctuation $[(C_{\text{max}}-C_{\min})/C_{\text{av}}]$ (Day 7)
- Swing $[(C_{\text{max}}-C_{\min})/C_{\min}]$ (Day 7)

The PK parameters will be estimated as follows:

- The C_{max} and the corresponding T_{max} , C_{\min} and C_{trough} will be read directly from the concentration-time plot (observed data, not predicted data by the program).
- AUCs will be calculated using the linear trapezoidal rule.
- The terminal elimination rate constant (K_{el}) will be determined by log linear regression obtained on at least the 3 last quantifiable concentrations and will not include C_{max} . The adjusted square of the correlation coefficient (R-square adjusted) for the goodness of fit of the regression line through the data points must be at least 0.80 for the K_{el} value to be considered reliable. If fewer than 3 quantifiable concentrations are available after C_{max} or if R-square is less than 0.80, the K_{el} will be left uncalculated.
- $t_{1/2}$ is calculated by the program as $\ln 2 / K_{\text{el}}$. If K_{el} is not calculable, then $t_{1/2}$ will also remain missing.
- The AUC from 0 to infinity is calculated by the program as:

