8.4 DATA SUMMARIZATION

PK parameters and plasma concentration data will be summarized by treatment using the following descriptive statistics (Table 2):

Table 2. PK Summary Statistics

Variable	Summarized with:
Plasma concentration at each time point	n, arithmetic mean, SD, CV%, minimum, median and maximum
AUCs, C _{max} , C _{min} , C _{trough} , C _{av}	n, arithmetic mean, SD, CV% (calculated as 100%*SD/mean), minimum, median, maximum, geometric mean and geometric CV% (calculated as $CV = 100\% \times \sqrt{e^{z^2} - 1}$, where z^2 is the variance of ln(PK parameter))
t _{1/2} , K _{el} , T _{max} , degree of fluctuation, swing	n, arithmetic mean, SD, CV%, minimum, median, maximum

Samples taken outside the sampling windows may be excluded from by-time point summary statistics; this will be determined prior to unblinding.

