¹Mean calculated based on number of subjects (N).

Programming Note: X will be assigned as 1, 2, 3.... as per each RP3128 dose level. Time point may vary depending the actual data.

<Dose Level> = RP3128 25mg, 100mg, 400mg in MAD

Table 14.2.1.2.X.S RP3128 – Summary of PK Parameters (SAD)

**PK Population
<Dose Level>**

Cohort/Subject	AUC _{0-t} (h*ng/mL)	AUC _{0-inf} (h*ng/mL)	C _{max} (ng/mL)	T _{max} (h)	K _{el} (1/h)	T _{1/2} (h)
xxxx	xxx	Xxx	xxx	xxx	xxx	xxx
xxxx	xxx	Xxx	xxx	xxx	xxx	xxx
....	xxx	Xxx	xxx	xxx	xxx	xxx
Statistics						
N	xx	xx	xx	xx	xx	xx
Mean	xxx.x	xxx.x	xxx.x	xxx.x	xxx.x	xxx.x
SD	xxx.xx	xxx.xx	xxx.xx	xxx.xx	xxx.xx	xxx.xx
CV (%)	xx.x	xx.x	xx.x	xx.x	xx.x	xx.x
Minimum	xxx	xxx	xxx	xxx	xxx	xxx
Median	xxx.x	xxx.x	xxx.x	xxx.x	xxx.x	xxx.x
Maximum	xxx	xxx	xxx	xxx	xxx	xxx
Geo Mean ¹	xxx.x	xxx.x	xxx.x	NA	NA	NA
Geometric CV%	xx.x	xx.x	xx.x	NA	NA	NA

N=Number of subjects with derivable PK parameter.

<Dose Level> = RP3128 25 mg, 50 mg, 100 mg, 200 mg, 400 mg

Programming Notes: Geometric mean shall be calculated for all PK parameters except T_{max}, t_{1/2} and K_{el}. T_{max} will only have n, median, min, max provided.

X will be assigned as 1, 2, 3.... as per each RP3128 dose level.

**Table 14.2.1.2.1.X.M RP3128 – Summary of PK parameters (MAD) – Day 1
PK Population
<Dose Level>**

Cohort/Subject	C _{max} (ng/mL)	AUC ₀₋₂₄ (ng·h/mL)	T _{max} (h)	T _{1/2} (h)
xxxx	xxx	xxx	xxx	xxx
xxxx	xxx	xxx	xxx	xxx
Statistics				
N	xx	xx	xx	xx
Mean	xxx.x	xxx.x	xxx.x	xxx.x
SD	xxx.xx	xxx.xx	xxx.xx	xxx.xx
CV (%)	xx.x	xx.x	xx.x	xx.x
Minimum	xxx	x.x	x.x	x.x
Median	xxx.x	xx.x	xx.x	xx.x
Maximum	xxx	x.x	x.x	x.x
Geo Mean ¹	xxx.x	xxx.x	NA	NA
Geometric CV%	xx.x	xx.x	NA	NA

N=Number of subjects with derivable PK parameter.

¹: Geo Mean: Geometric means are based on the arithmetic means of ln-transformed values

Programming Note: <Dose Level> = RP3128 25mg, 100mg, and 400mg.

X will be assigned as 1, 2, and 3 as per each RP3128 dose level.

**Table 14.2.1.2.2.X.M RP3128 – Summary of C_{trough} (MAD)
PK Population
<Dose Level>**

Cohort/Subject	C _{trough} (ng/mL)		
	Day 3	Day 5	Day 7
xxxx	xxx	xxx	xxx
xxxx	xxx	xxx	xxx
Statistics			
N	xx	xx	xx
Mean	xxx.x	xxx.x	xxx.x
SD	xxx.xx	xxx.xx	xxx.xx
CV (%)	xx.x	xx.x	xx.x
Minimum	xxx	xxx	x.x
Median	xxx.x	xxx.x	xx.x
Maximum	xxx	xxx	x.x
Geo Mean ¹	xxx.x	xxx.x	xxx.x
Geometric CV%	xx.x	xx.x	xx.x

N=Number of subjects with derivable PK parameter.

¹: Geo Mean: Geometric means are based on the arithmetic means of ln-transformed values

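### The multiple-dose PK objective is set at steady state, but the SAP names no analysis to judge whether seven daily doses reach it

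*SAP*

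**What the plan says.** SAP Section 3.2 gives the multiple-dose PK objective as "To characterize the multiple dose PK profile of oral RP3128 at steady state". Section 3.3 fixes the regimen: "multiple doses of RP3128/placebo were administered once a day from Day 1 to Day 7".

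Section 4.2 lists trough concentration on Days 3, 5 and 7 as an endpoint. It also lists Cmax, Tmax, AUC0-24 and half-life on Days 1 and 7, and Cmin, Cav, degree of fluctuation and swing on Day 7. Section 8.3.1 describes Cav as "Average concentration during the dosing interval" and ties it to Day 7. Section 8.4 keeps the analysis descriptive: "PK parameters and plasma concentration data will be summarized by treatment using the following descriptive statistics".

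The shell for Table 14.2.1.2.2.X.M has one row per subject, with adjacent trough columns for Days 3, 5 and 7. Day 1 and Day 7 AUC0-24 are in two separate tables. The SAP text does not mention steady state outside Section 3.2.

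Two data rules also matter here. Section 8.2 and Appendix C (footnote 15) give no time within the day for the Day 3 and Day 5 samples, while Day 7 has both a pre-dose and a 24 h sample. Section 8.3.2 contains a rule that sets samples taken before dosing to zero, without saying before which dose.

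**The concern.** The Day 7 parameters are the main planned outputs that can answer the steady-state objective, and they do so only if the seventh dosing interval is close to steady state. The SAP does not say which output decides that, what comparison is made across days, or what happens to the wording if the answer is no. If the half-life is long relative to seven daily doses, Day 7 AUC0-24 and Cav fall below their steady-state values, while fluctuation and swing lie above theirs. A report following this plan could present those figures as the steady-state profile without having examined the question.

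The informal look that the trough table allows is also insecure. The three columns may not be on the same basis, and the zero rule, read literally, would remove the Day 7 pre-dose value.

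**Working it through.** The SAP states no half-life, time to steady state or accumulation figure, so there is nothing to reproduce. The half-lives below are assumptions shown as a range.

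**Inputs from the SAP.** Dosing interval 24 h and seven doses (Section 3.3); six active subjects per multiple-dose cohort (Section 3.6).

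**Step 1: approach to steady state.** With linear kinetics, the share of steady state reached in the interval after dose n is f(n) = 1 − 2^(−24n/t½). For the Day 7 interval n = 7, so f(7) = 1 − 2^(−168/t½). At 48 h, for example, f(7) = 1 − 2^(−3.5) = 0.912. The pre-dose trough on Day 5 follows four doses and that on Day 7 follows six.

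| Assumed t½ | Day 7 interval, f(7) | Day 5 pre-dose, f(4) | Day 7 pre-dose, f(6) | Day 7/Day 5 trough, f(6)/f(4) | 24 h after dose 7 / Day 7 pre-dose, f(7)/f(6) | AUC0-24 ratio Day 7/Day 1, f(7)/f(1) | Same ratio at full steady state, 1/f(1) |
|---|---|---|---|---|---|---|---|
| 24 h | 0.992 | 0.938 | 0.984 | 1.05 | 1.01 | 1.98 | 2.00 |
| 48 h | 0.912 | 0.750 | 0.875 | 1.17 | 1.04 | 3.11 | 3.41 |
| 72 h | 0.802 | 0.603 | 0.750 | 1.24 | 1.07 | 3.89 | 4.85 |
| 96 h | 0.703 | 0.500 | 0.646 | 1.29 | 1.09 | 4.42 | 6.29 |

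Solving f(7) ≥ 0.90 gives t½ ≤ 168·ln 2/ln 10 ≈ 51 h. Solving f(7) ≥ 0.95 gives t½ ≤ 168·ln 2/ln 20 ≈ 39 h.

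**Step 2: fluctuation and swing.** One-compartment oral superposition with an assumed absorption rate of 1/h gives Day 7 against true steady state as follows:
- at 48 h, fluctuation 0.32 against 0.28 and swing 0.39 against 0.33;
- at 72 h, fluctuation 0.25 against 0.19 and swing 0.29 against 0.21.

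**Step 3: which ratio is informative.** Comparing the last two troughs, one day apart, gives 1.04 to 1.09 at half-lives of 48 to 96 h, where only 91% to 70% of steady state is reached. The Day 7/Day 5 pre-dose ratio over the same range is 1.17 to 1.29. The accumulation ratio must be read with the half-life: 3.11 is close to complete at 48 h only because the full value there is 3.41.

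**Step 4: basis of the troughs.** If Day 5 is pre-dose but the Day 7 trough is taken 24 h after dose 7, the ratio at 72 h becomes 0.802/0.603 = 1.33 instead of 1.24, for the same kinetics.

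**Step 5: precision.** With six subjects and within-subject CV on the raw scale, s = √ln(1 + CV²), and the 90% CI multiplies the ratio by exp(± 2.015·s·√2/√6). Around a ratio of 1 this is 0.89 to 1.12 at an assumed CV of 10%, and 0.71 to 1.41 at 30%. Around 1.243 (72 h) it is 1.11 to 1.40 and 0.88 to 1.75 respectively.

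**Step 6: the zero rule.** If the Day 7 pre-dose value is set to zero, the trough ratio is zero and cannot enter a geometric mean. If Day 5 is also pre-dose, the ratio is 0/0.

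**The case against.** The strongest reply is that the material for a check is already planned. Troughs on three days are a named endpoint, set out side by side for each subject, and half-life is tabulated for both parts. A Day 7/Day 5 trough ratio of 1.17 to 1.24 would be visible there. This stands: the plan does not leave the question without data. It lacks a designated assessment and a stated consequence.

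A reader might infer that the Day 7 parameters are mislabelled as steady-state quantities. The SAP does not support that, because Sections 4.2 and 8.3.1 and the shells label them by day and dosing interval only.

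A reader might also infer a long half-life from sampling to 192 h after the last multiple dose, or to 336 h after a single dose. Late sampling shows only that the design allows for one. Section 3.7 says the multiple-dose levels were set considering single-dose PK, and whether seven days is long enough is a design matter that the protocol may cover.

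On the zero rule, the sentence introducing that list in Section 8.3.2 concerns samples without a quantifiable concentration, so a narrow reading is possible. But the preceding item already covers unquantifiable pre-dose samples, so the separate item on all samples before dosing either repeats it or reaches further. The text needs to settle this.

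Finally, six active subjects per cohort cannot support a firm test. That is correct, and it argues for an estimate with an interval and against a pass/fail rule.

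**Conclusion.** The concern holds in a limited form. The objective names steady state, no analysis is specified as its assessment, no accumulation ratio is planned, and nothing says how Day 7 results are described if steady state is not reached.

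The size depends wholly on a half-life the SAP does not give. The shortfall in Day 7 exposure is about 1% at 24 h and 9% at 48 h, rising to 20% at 72 h and 30% at 96 h, assuming linear kinetics. If the half-life is below about 39 h, Day 7 is within 5% of steady state and the gap has little practical effect.

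The point concerns a secondary, descriptive objective. It is worth correcting because the remedy is cheap and lets the study answer the question it poses.

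**What to change.** All changes use samples already planned.

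1. Name Table 14.2.1.2.2.X.M as the steady-state assessment. State that the Day 3, Day 5 and Day 7 troughs are all pre-dose samples, and put those times in Section 8.2 and Appendix C.
2. In Section 8.3.2, restrict the rule setting pre-dose concentrations to zero to samples taken before the first dose.
3. By dose level, add the within-subject Day 7/Day 5 pre-dose trough ratio and the Day 7/Day 1 AUC0-24 accumulation ratio, as geometric means with 90% CIs. Read them with the estimated half-life and present them as estimates. Half-life is in Section 4.2 and the table shells but missing from the multiple-dose list in Section 8.3.1, so add it there.
4. Describe the parameters as Day 7 values unless these results support steady state, and say so in the SAP.

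A mixed model is not needed. A rule that the last two troughs have a ratio close to 1 should not be used, because it is insensitive (Step 3 of the working).

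The cost is a little more analysis and intervals that will be wide with six subjects. The steady-state wording may also have to be dropped from the report.

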3.3 BRIEF DESCRIPTION

This is a phase I, single-center, double-blind, randomized, placebo-controlled study to evaluate the safety, tolerability, and PK of single or multiple ascending dose (SAD or MAD) of RP3128 in healthy volunteers.

There were 5 cohorts in SAD and 3 cohorts in MAD. In the first part of the study (Part 1, SAD), single dose of RP3128/placebo was administered on Day 1. In the second part (Part 2, MAD), multiple doses of RP3128/placebo were administered once a day from Day 1 to Day 7. In both SAD and MAD, the cohorts were dosed sequentially so that a minimum of 8 days was allowed between dose of previous cohort and the initiation of next cohort. Progression to the next higher dose occurred only after confirming safety, tolerability and PK of existing dose. In case of safety concern, additional subjects may be added to cohort for safety assessment as per the decision of Safety Review Committee (SRC).

In addition, sentinel design was applied. Within each cohort, 2 sentinel subjects was dosed first for safety assessment. Safety and tolerability data up to 24 hours was reviewed along with any observation up to 36 hours by the investigator prior to dosing the remaining subjects at that dose level. The remainder of the cohort was dosed sequentially at least 48 hours after confirming safety and tolerability of sentinel cohort.

3.4 SUBJECT SELECTION

Healthy male subjects and female subjects of non-childbearing between the ages of 18 and 45 years were randomized at the study site.

All subjects must give written informed consent to be enrolled into the study. Subjects were considered eligible to participate in this study if all inclusion criteria was satisfied and no exclusion criteria was met at screening. Please refer to the Protocol for detailed inclusion/exclusion criteria.

